6.1.1.3. Immunogenicity against the vector

For VNA against the vector, if available following statistics will be calculated: N, geometric mean^{§(see above for the calculation)} and corresponding 95% CI of the actual values.

Subject profiles of the assays against the insert will be repeated, highlighting subjects with pre-existing immunity at baseline against the vectors.

Scatterplots of the Adeno assay versus the assays against the inserts may be provided for the most important time points. In these scatterplots the actual values will be shown, even if they are below the LLOQ.

6.1.2. Handling of Missing and/or Unquantifiable Immune Response Data

Missing immune response data will not be imputed.

Depending on the assay, a LLOQ will be available, or a provisional cutoff will be set at the analysis level. Values below the LLOQ or cut-off will be treated as follows:

- Values will be imputed based on the type of analysis. For the calculation of the geometric mean titer, values below LLOQ will be imputed to LLOQ/2. While for the calculation of the geometric mean of the increase from baseline, values below LLOQ will be imputed to LLOQ. The LLOQ values per assay are available in the database.

For ICS: if no LLOQ is available for a certain ICS cytokine combination (e.g., total cytokine response, Th1/2, etc.) at the time of analysis, a provisional lower limit of 0.001% will be used to impute as described above

- For all assays: values above the upper limit of quantification (ULOQ) will be imputed with ULOQ.

7. REGIMEN SELECTION RULE

7.1. Immunogenicity Analysis

The objective is to compare the RSV A2 neutralizing antibody levels of all regimens containing RSV preF protein (Groups 12 through 17) to the one-dose Ad26.RSV.preF regimen (Group 11). This will be based on the estimation of GMT ratios and corresponding 95% confidence intervals (CIs) of the VNA A2 levels of the regimens containing RSV preF protein on Day 29 for the one-dose regimens (Groups 12 through 16) and on Day 85 for the two-dose regimen (Group 17) versus the VNA A2 levels on Day 29 of the one-dose Ad26.RSV.preF regimen (Group 11).

Additional factors such as data from other assays, cost of goods, and ease of administration will be taken into account to select the regimen for the expanded safety phase.

ATTACHMENTS**ATTACHMENT 1: Toxicity Tables**

Adapted from the FDA Guidance document “Toxicity Grading Scale for Healthy Adult and Adolescent Volunteers Enrolled in Preventive Vaccine Clinical Trials” (September 2007).

The grading scale used for laboratory assessments is based on the FDA Guidance document “Toxicity Grading Scale from Healthy Adult and Adolescent Volunteers Enrolled in Preventive Vaccine Clinical Trials”. Any laboratory value shown as a “graded” value in the table that is within the central laboratory normal ranges will not be graded for severity or recorded as an AE. For hemoglobin, both the actual value and the change from reference will be graded. For the change from reference, the corresponding actual value should also be at least Grade 1

Blood, Serum, or Plasma *	Mild (Grade 1)	Moderate (Grade 2)	Severe (Grade 3)	Potentially Life Threatening (Grade 4) **
Sodium – Hyponatremia mmol/L	132 – 134	130 – 131	125-129	< 125
Sodium – Hypertremia mmol/L	144-145	146 – 147	148-150	>150
Potassium – Hyperkalemia mmol/L	5.1 – 5.2	5.3 – 5.4	5.5-5.6	>5.6
Potassium – Hypokalemia mmol/L	3.5-3.6	3.3-3.40	3.1-3.2	<3.1
Glucose – Hypoglycemia mmol/L	3.83-3.61	<3.61-3.05	<3.05-2.5	<2.5
Glucose – Hyperglycemia Fasting – mmol/L	5.55-6.11	>6.11-6.94	>6.94	Insulin requirements or hyperosmolar coma
Glucose – Hyperglycemia Random – mmol/L	6.11-6.94	>6.94-11.10	>11.10	
Blood Urea Nitrogen mmol/L	8.2-9.3	>9.3 – 11.1	> 11.1	Requires dialysis
Creatinine – umol/L	133 – 150	>150 – 177	>177-221	>221 or requires dialysis
Calcium – hypocalcemia mmol/L	2.10-2.00	<2.00-1.87	<1.87-1.75	<1.75
Calcium – hypercalcemia mmol/L	2.62-2.74	>2.74-2.87	>2.87-3	3
Magnesium – hypomagnesemia mmol/L	0.62-0.53	<0.53-0.45	<0.45-0.37	<0.37
Phosphorous – hypophosphatemia mmol/L	0.81-0.74	<0.74-0.65	<0.65-0.52	0.52
CPK – mg/dL	1.25-1.5xULN	1.6-3.0xUNL	3.1-10xULN	>10 x ULN***
Albumin – Hypoalbuminemia g/L	31-28	<28-25	<25	--
Total Protein – Hypoproteinemia g/L	60-55	<55-50	<50	--
Alkaline phosphate – U/L	1.1 – 2xULN	2.1-3xULN	3.1-10xULN	> 10 x ULN
AST U/L	1.1-2.5xULN	2.6-5xULN	5.1-10xULN	>10 x ULN

Blood, Serum, or Plasma *	Mild (Grade 1)	Moderate (Grade 2)	Severe (Grade 3)	Potentially Life Threatening (Grade 4) **
ALT U/L	1.1-2.5xULN	2.6-5xULN	5.1-10xULN	>10 x ULN
Bilirubin – when LFT is normal	1.1-1.5xULN	1.6-2.0xULN	2.0-3.0 x ULN	>3.0 x ULN
Bilirubin – accompanied by graded LFT (ALT or AST)	1.1-1.25xULN	1.26-1.5xULN	1.51-1.75 x ULN	> 1.75 x ULN
Amylase- U/L	1.1-1.5xULN.	1.6-2.0xULN	2.1 – 5.0 x ULN	> 5.0 x ULN
Lipase- U/L	1.1-1.5xULN	1.6-2.0xULN	2.1 – 5.0 x ULN	> 5.0 x ULN
Cholesterol – mmol/L	64.89-67.80	>67.80-72.64	>72.64	--
Hemoglobin (Female) - g/L	110 – 120	95 – 109	80 – 94	< 80
Hemoglobin (Female) change from baseline value- g/L	Any decrease – 15	16-20	21 – 50	> 50
Hemoglobin (Male) - g/L	125 -135	105 – 124	85 – 104	< 85
Hemoglobin (Male) change from baseline value - g/L	Any decrease – 15	16-20	21 – 50	> 50
WBC Increase – 10E9/L	10.8-15.0	>15.0-20.0	>20.0-25	>25
WBC Decrease - 10E9/L	3.5-2.5	<2.5-1.5	1-<1.5	<1
Lymphocytes Decrease - 10E9/L	1.00-0.75	<0.75-0.50	<0.50-0.25	<0.25
Neutrophils Decrease - 10E9/L	2.0-1.5	<1.5-1.0	<1.0-0.5	<0.5
Eosinophils - 10E9/L	0.65-1.50	>1.50-5.00	>5.00	Hypereosinophilic
Platelets Decreased - 10E9/L	140-125	<125-100	<100-25	<25
PT – seconds (prothrombin time)	1.0-1.10xULN	1.11-1.20xULN	1.21-1.25xULN	>1.25xULN
PTT – seconds (partial thromboplastin time)	1.0-1.2xULN	1.21-1.4xULN	>1.41-1.5xULN	> 1.5 x ULN
Fibrinogen increase – umol/L	11.76-14.70	>14.70-17.65	>17.65	--
Fibrinogen decrease - umol/L	5.88-4.41	<4.41-3.68	<3.68-2.94	<2.94 or associated with gross bleeding or disseminated intravascular coagulation (DIC)

* The laboratory values provided in the tables serve as guidelines and are dependent upon institutional normal parameters. Institutional normal reference ranges should be provided to demonstrate that they are appropriate.

** The clinical signs or symptoms associated with laboratory abnormalities might result in characterization of the laboratory abnormalities as Potentially Life Threatening (Grade 4). For example, a low sodium value that falls within a grade 3 parameter (125-129 mE/L) should be recorded as a grade 4 hyponatremia event if the subject had a new seizure associated with the low sodium value.

***" ULN" is the upper limit of the normal range.

Vital Signs *	Mild (Grade 1)	Moderate (Grade 2)	Severe (Grade 3)	Potentially Life Threatening (Grade 4)
Fever (°C) ** (°F) *	38.0 – 38.4 100.4 – 101.1	38.5 – 38.9 101.2 – 102.0	39.0 – 40 102.1 – 104	> 40 > 104
Tachycardia - beats per minute	101 – 115	116 – 130	> 130	ER visit or hospitalization for arrhythmia
Bradycardia - beats per minute***	50 – 54	45 – 49	< 45	ER visit or hospitalization for arrhythmia
Hypertension (systolic) - mm Hg	141 – 150	151 – 160	> 160	ER visit or hospitalization for malignant hypertension
Hypertension (diastolic) - mm Hg	91 – 95	96 – 100	> 100	ER visit or hospitalization for malignant hypertension
Hypotension (systolic) – mm Hg	85 – 89	80 – 84	< 80	ER visit or hospitalization for hypotensive shock
Respiratory Rate – breaths per minute	17 – 20	21 – 25	> 25	Intubation

* Subject should be at rest for all vital sign measurements.

** Oral temperature; no recent hot or cold beverages or smoking.

*** When resting heart rate is between 60 - 100 beats per minute. Use clinical judgement when characterizing bradycardia among some healthy subject populations, for example, conditioned athletes.

ATTACHMENT 2: Transforming Solicited AE data into Analysis Format

Solicited AEs diary and onsite data in the SDTM FA and SR domains will both be remapped to the SDTM CE domain. They will be recorded by event in the CE domain, like the format of unsolicited AEs. The reported start date of an AE in the CE domain will be the date of first occurrence of the solicited AE. The last reported date will be used as the end date of the AE, regardless of possible changes in grade or time gaps, and taking into account if the AE continues after Day 8. The grade of the solicited AE (in CE) will be the maximum grade over the duration of the AE reporting period.

The derivation of the solicited AE ADAM dataset from SDTM CE will follow a similar approach to the derivation of the unsolicited AE ADAM dataset from SDTM AE. For observed solicited AE(s), one record per AE type will be derived per participant per post-dose period, pooling both onsite and diary records in the SDTM CE data. The start date of an AE will be derived as the first occurrence of that AE type (pooling the onsite and diary record) for a participant. The end date will be derived as the last end date between the onsite and diary record. The duration of a solicited AE will be recalculated in the ADAM dataset as: the derived end date – derived onset date + 1.

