11.2. Sample Size Determination

11.2.1. Initial Safety Cohort (Cohort 1)

The number of participants chosen for the initial safety cohort will provide a preliminary safety assessment. Placebo recipients are included for blinding and safety purposes and will provide additional control specimens for immunogenicity assays.

While mild to moderate vaccine reactions (local injection site, systemic responses) are expected, AEs that preclude further vaccine administration or more serious ones that would limit product development are not anticipated.

Table 18 shows the probabilities of observing at least one AE in the initial safety cohort at given true AE rates. In the analysis of the initial safety cohort (Cohort 1), placebo recipients will be shown pooled.

Table 18: Probability of Observing at Least One Adverse Event in the Initial Safety Cohort (Cohort 1) at a Given True Adverse Event Rate

True Adverse Event Rate	Probability of Observing at Least One Adverse Event in N Participants		
	N=4	N=8	N=16
0.5%	2%	4%	8%
1%	4%	8%	15%
2.5%	10%	18%	33%
5%	19%	34%	56%
10%	34%	57%	81%
25%	68%	90%	99%
50%	94%	100%	100%

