5. SAFETY

Safety analyses will be performed on the FA set. Continuous variables will be summarized using the following statistics, as appropriate: number of observations, median, quartiles (Q1 and Q3), minimum and maximum. Frequencies and percentages (one decimal place) will be generated for categorical variables. No formal comparisons between groups will be provided.

One type of safety tables will be shown. The by regimen layout, safety data will be analysed by vaccine regimens as designed per protocol and data will be presented by period. Denominator for the percentages is the number of subjects with considered data in the considered population and period for a certain regimen (incidence per 100 subjects/period).

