5.1. Adverse Events (AE)

5.1.1. Definitions

Solicited AEs shown in the tables and listings will be extracted from the SDTM CE domain which will be based on the diary pages and onsite assessment pages of the CRF ([ATTACHMENT 2](#)). When participants are given two injections in opposite arms at a given visit, then local solicited AEs will be collected and reported for both arms separately. For unsolicited AEs, only AEs with start date (grade and/or relation) within the 28-day period following vaccination will be presented in the safety tables except for SAEs, which will be captured and tabulated in the outputs covering the whole study period. All other unsolicited adverse events collected outside this 28-day period will be presented through listings. Any RTI recorded as an AE in the eCRF will be excluded from any AE analysis if the central laboratory RT-PCR is subsequently found to be positive for RSV.

Solicited local AEs will be by definition considered as related to the study vaccine.

The severity of the AEs will be classified as grade 1 to 4. Solicited events that are graded less than grade 1, are not considered as AE.

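### SAP Attachment 2 has no arm key for local solicited AEs, so as written it cannot deliver the by-arm reporting that SAP 5.1.1 requires at two-injection visits

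*SAP*

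**What the plan says.** SAP 5.1.1 sets the reporting rule. Where a participant has two injections in opposite arms at one visit, "local solicited AEs will be collected and reported for both arms separately". The same section states "Solicited AEs shown in the tables and listings will be extracted from the SDTM CE domain" and refers the reader to Attachment 2 for how those data are built.

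Attachment 2 then describes the analysis dataset: "one record per AE type will be derived per participant per post-dose period, pooling both onsite and diary records". On onset it says "The start date of an AE will be derived as the first occurrence of that AE type", taken at participant level across the onsite and diary records. The end is the later of the onsite and diary end dates, and duration is end minus onset plus one day. Arm and injection site are not mentioned anywhere in the attachment.

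Elsewhere, SAP 5.1.5 lists three local event types (erythema, induration/swelling, pain/tenderness) without splitting them by arm. SAP 5 states "One type of safety tables will be shown", a by-regimen layout. SAP 5.1.2 asks for solicited events by worst grade and, for the most frequent ones, time to onset and duration. Both 5.1.1 and Attachment 2 are listed among the sections changed by SAP Amendment 3, so both are current text.

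**The concern.** Two parts of the SAP give different units for the same data. Section 5.1.1 works with the arm. Attachment 2 identifies a record by participant, period and event type. A programmer who follows Attachment 2 to the letter ends with one pain record for a participant who had pain in both arms, and no variable to split it.

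Solicited local AEs within 7 days of vaccination are a primary endpoint in every cohort (Protocol 2.1). The two-injection design also makes the arm informative. In most of Cohort 2 one arm is a within-person placebo control. Group 16 is the only Cohort 2 group that receives the two products in separate arms. A single record per event type hides both contrasts and can join two short reactions into one long one.

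**Working it through.** **1. Cohort 2 total.** Group sizes from Protocol Table 9 (Groups 11 to 18): 24 + 42 + 42 + 42 + 42 + 36 + 36 + 24 = 288, the stated total. The allocation ratio in Protocol 5, 4:7:7:7:7:6:6:4, sums to 48; 288/48 = 6 per unit, which returns the same group sizes.

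**2. What merges on Day 1.** Every Cohort 2 group has two Day 1 injections in opposite arms (Protocol Table 9).

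| Day 1 content of the two arms | Groups | n | Share of 288 |
|---|---|---|---|
| Active + placebo | 11–15, 17 | 24 + 4×42 + 36 = 228 | 79.2% |
| Ad26 + protein | 16 | 36 | 12.5% |
| Placebo + placebo | 18 | 24 | 8.3% |

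In Cohort 1 (Protocol Table 8), Groups 8, 9 and 10 have opposite-arm injections on Day 1 and at Month 12: 4 + 8 + 8 = 20. Group 8 is placebo + placebo, Group 9 active + placebo, Group 10 Ad26 + protein. Cohort 3 is not counted, because the documents do not say how many injections per visit the selected regimen needs.

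**3. What each output needs.**

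- Any-arm incidence per participant needs only one record per event type. Attachment 2 supplies it.
- By-arm incidence needs an arm variable. Attachment 2 has none.
- By-arm onset needs the first date within arm. Attachment 2 keeps the first date over the participant.
- By-arm duration needs start and end within arm. Attachment 2 keeps the earliest start and the latest end. As a hypothetical case at the edges of the diary period, a one-day reaction on Day 1 in one arm and a one-day reaction on Day 8 in the other give a merged duration of 8 − 1 + 1 = 8 days, although each lasted one day. Attachment 2 deliberately bridges time gaps within an event; without an arm key the bridging also runs across two injection sites.
- Grade: the maximum-grade sentence in Attachment 2 concerns the SDTM CE domain. The paragraph on the analysis dataset gives no grade rule for records that are combined.

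**4. Size of the difference between any-arm and active-arm incidence.** The documents give no local reaction rates, so these are assumptions: a = 50% in the active arm, p = 10 to 30% in the other.

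- Full overlap (everyone who reacts in the other arm also reacts in the active arm): any-arm rate = max(a, p) = 50%, an excess of 0 points.
- Independent arms: any-arm rate = a + p − ap.
  - p = 10%: 0.50 + 0.10 − 0.05 = 55%, excess 5 points.
  - p = 20%: 0.50 + 0.20 − 0.10 = 60%, excess 10 points.
  - p = 30%: 0.50 + 0.30 − 0.15 = 65%, excess 15 points.

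The range is therefore 0 to 15 points. It rests on the assumed rates and on overlap lying between independence and complete. Less overlap than independence would give more.

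**The case against.** The strongest reply is that Attachment 2 never says arms are merged. What it expressly pools is two data sources, onsite assessment and diary. Event type is undefined, so pain in the left arm and pain in the right arm could count as two types, and 5.1.1, which points to Attachment 2, could supply the missing arm rule. That reading is possible, but the SAP does not state it. The key remains participant, period and type, onset is set at participant level, and 5.1.5 lists three local types only. A possible reading is not a specification.

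Several replies stand in full, and they rule out stronger inferences a reader might draw.

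- *That active and placebo reactions merge in all of Cohort 2.* Groups 16 and 18 (60 participants) have no active/placebo pair. The figure is 228 of 288.
- *That arm-level information is lost.* Local events are to be collected by arm (SAP 5.1.1), and the injected arm is recorded in the eCRF (Protocol 6). The gap is in the derived dataset and can be repaired from source.
- *That regimen comparisons are biased.* The table layout is by regimen, and in Cohort 2 the Day 1 regimen includes both injections. All eight groups, placebo included, receive two, so Day 1 any-arm comparisons within Cohort 2 are like for like. The any-arm rate overstates only if it is read as the rate for the active injection.
- *That Attachment 2 also distorts the pooled Cohort 1 placebo column.* That pooling is a separate choice stated in Protocol 11.2.1 ("placebo recipients will be shown pooled"). Attachment 2 does not cause it, and an arm key would not change who is pooled.

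**Conclusion.** The inconsistency is real and worth correcting. As specified, the analysis dataset cannot yield the by-arm incidence, onset or duration that 5.1.1 implies for the 288 Cohort 2 participants on Day 1 and for the 20 in Cohort 1 Groups 8 to 10 on Day 1 and at Month 12. Any-arm incidence by regimen is unaffected.

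The practical weight is moderate. The endpoint is primary, but the safety analysis is descriptive with no formal comparisons (SAP 1.3 and 5), and the source data are to be collected by arm. The numerical effect cannot be taken from the documents: 0 to about 15 points holds only under the rates and overlap assumed above. A reader might take the upper end as a demonstrated overstatement of local reactogenicity; nothing in the protocol or SAP supports that.

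**What to change.** In Attachment 2, add injection site (arm) to the record key for local solicited events, so that a record is identified by participant, post-dose period, event type and arm. State that start, end, duration and grade are derived within arm. State that any participant-level any-arm row takes the worst grade over the two arms. In 5.1.2 or 5.1.5, say which local tables are shown by arm and which are any-arm.

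Tables by product (active versus placebo arm; in Group 16, Ad26 versus protein arm) go beyond what 5.1.1 requires. They need a link from product to arm, and the documents show only that the injected arm is recorded. Make them conditional on that link being available after unblinding.

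The cost is a few sentences in the SAP, one extra key in the dataset and the matching table shells. The by-arm tables need no new data.
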